The current study is not designed to prove non-inferiority, but serves as a pilot study to evaluate if non-inferiority is observed for the two novel treatment regimes compared to the current treatment regime. As many as possible IR patients matching the inclusion criteria (see above) will be recruited during the recruitment period. Based on previous experience in the center, the expected total number of IR patients equals 120 taking into account a recruitment period of three years. If it is possible to include 120 patients before the time frame of three years has finished, recruitment will be stopped earlier. If by any unforeseen circumstances, after three years still not enough patients are included in the study, recruitment will be running until a total number of 120 patients will be obtained.

Note:

A drop out rate of 10% due to concomitant infection, loss of follow-up or non-related adverse events is possible during the setting.

D. Statistics

A linear model for longitudinal measures (More specifically, a direct likelihood approach is adopted using an unstructured covariance matrix (Molenberghs and Kenward, 2007, Section 14.4)¹) will be used to compare the evolution of VAS, RQLQ and drop in PNIF between the four groups, with the baseline value as a covariate. A transformation of the outcome will be considered when needed to handle skewness in the distribution of the model residuals. Differences between the groups will be compared with the a-priori defined regions of equivalence (see section Outcomes). 95% confidence intervals for differences at specific time points will be reported. Note again that the aim of this pilot study is to describe the pattern of the differences, and not to prove non-inferiority based on these confidence intervals. For the evaluation of the TRE, a

¹ G. Molenberghs and M.G. Kenward. Missing Data in Clinical Studies. Hoboken, NJ : John Wiley & Sons, 2007.

logistic regression model using generalized estimating equations (GEE)² will be used to compare the evolution in proportion patients free of complaints (TRE score 5), with the baseline TRE score as covariate.

E. Patient recruitment

Patients will be enrolled by four different strategies:

- Patients with a new diagnosis of IR who visit the ENT department at the University Hospital of Leuven will be offered the possibility to take part in this study and will be screened for in- and exclusion criteria.

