As this study will include four parallel arms of equal sample size, the 120 included IR patients will be randomized in four equal groups of each 30 patients (n=30 patients per treatment arm). A block randomization with varying block sizes will be used.

G. Demographic and clinical information

Patient's demographic information as well as general medical history will be gathered from medical records and verified during the screening visit to the Outpatient clinic.

Demographic data of importance are: age, gender, smoking, occupation, exposure to agents during professional or recreational activity, concomitant bronchial disease (asthma, COPD), aspirin intolerance and current medication use.

The respective information is gathered in case report forms (CRFs) and will be analyzed by GraphPad Prism 6.

H. Time schedule and visit table

[figure not shown]

Table 2: Schematic visualization of the timeframe and visit table

As demonstrated in table 1, the included patients will visit the ENT Department of UZ Leuven at six occasions.

- Screening visit (week -3)

Explanation of study, study protocol and treatment.

Inclusion in study after signing the informed consent form.

Evaluation of inclusion and exclusion criteria.

Pregnancy test for women with childbearing potential.

Skin prick test for common aero-allergens if not yet performed.

Blood tests for total and/or specific IgE.

Nasal endoscopy for exclusion of anatomic deformities, rhinosinusitis or nasal polyps.

Symptom evaluation using VAS scores for individual and total nasal symptoms.

Quality of life evaluation using the rhinitis quality of life questionnaire (RQLQ).

- Baseline visit (week -1):

Re-evaluation of the inclusion and exclusion criteria.

Clinical nasal examination including nasal endoscopy.

NHR challenge (by CDA provocation and/or hyperosmolar discs).

Nasal fluid collection before and after NHR challenge.

Evaluation of nasal airflow by peak nasal inspiratory flow (PNIF) device before and after NHR provocation.

Symptom evaluation using VAS scores for individual and total nasal symptoms.

Quality of life evaluation using the rhinitis quality of life questionnaire (RQLQ).

- Randomization and start of treatment (week 0):

Explanation treatment i.e. five applications of capsaicin/placebo nasal spray with a one-hour interval, followed by handing over the capsaicin nasal spray or placebo for the following four weeks.

Brief nasal examination.

Evaluation of adverse events.

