On the day of the treatment, all IR patients will be treated by [name]. [name], [name] [name], Apr. [name] or CTA [name] with a blinded nasal spray (capsaicin or placebo) five times with one-hour intervals as described by the treatment protocol of Van Rijswijk et al. (13). The nasal mucosa of all patients will be anaesthetized prior to the first three applications by 2 puffs of cocaine 5% nasal spray in each nostril. To ensure effective local anesthesia, an interval of 10 to 15 minutes was maintained.

To protect the eyes of the patients against potential irritating particles of capsaicin, all individuals will be suggested to close their eyes during the application of capsaicin nasal spray.

After finalizing the treatment protocol, the patient will be handed over a nasal spray containing capsaicin 0,01mM, capsaicin 0,001mM or placebo to take home and to use for the consecutive four weeks, labeled with his/her allocated study number (Caps001-Caps120) and the usage (2 puffs in each nasal cavity once daily).

- Evaluation of nasal symptoms by VAS scores:

All patients will be asked to mark the typical nasal symptoms on a visual analogue scale for individual (INS) and total nasal symptoms (TNS) before treatment and at week 4, 12 and 26. A visual analogue scale is a measurement of a patient's subjective evaluation of symptom severity by indicating a position on a line between two endpoints, which represent a well-validated and easy technique of the evaluation of symptom severity. Indeed, VAS scores for TNS have recently been validated and proposed as a means of evaluation of symptom control in rhinitis (20).

- Evaluation of quality of life by Rhinitis Quality of Life Questionnaire:

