Functional problems that are most troublesome to adults with rhinitis will be measured by the RQLQ by 28 questions in 7 domains (activity limitation, sleep problems, nose symptoms, eye symptoms, non-nose/eye symptoms, practical problems and emotional function). There are three 'patient-specific' questions in the activity domain, which allow patients to select three activities in which they are most limited by their rhinitis. Patients recall how bothered they have been by their rhinitis during the previous week and to respond to each question on a 7-point scale (0 = not impaired at all and 6 = severely impaired). The overall RQLQ score is the mean of all 28 responses and the individual domain scores are the means of the items in those domains. The RQLQ has excellent measurement properties and has been used extensively throughout the world both in clinical practice and clinical trials. The validation studies have shown that these properties are very similar to

those found for the Asthma Quality of Life Questionnaire (21). Patients will be asked to score RQLQ before treatment and at week 4, 12 and 26.

- Adherence evaluation:

Patients will be asked to bring their nasal spray with them on follow up visit 2 at week 4. Weighing the residual fluid on day 28 will objectively check adherence.

All patients will be asked to write down their symptoms, adverse events and degree of sensitization/desensitization in a dairy (see addendum). The diary will be handed over to them at the day of the treatment.

- Therapeutic Response Evaluation (TRE):

TRE will be measured on a 1 to 5 scale.

- 5 klachten zijn volledig verdwenen = klachtnvrij
- 4 klachten zijn bijna volledig verdwenen
- 3 klachten zijn verminderd, doch nog aanwezig
- 2 klachten zijn licht verminderd, doch nog sterk aanwezig
- 1 klachten zijn onveranderd ten opzichte van vóór de behandeling

Patients will be asked to score their symptom relief on week 4, week 12 and week 26.

- Evaluation of recurrence of symptoms:

The recurrence of symptoms will be measured on a 1 to 5 scale.

- 5 klachten zijn volledig terug aanwezig
- 4 klachten zijn voor een aanzienlijk deel terug aanwezig
- 3 klachten zijn nog steeds duidelijk verminderd
- 2 klachten zijn licht verminderd, doch beginnen terug te keren
- 1 klachten zijn nog steeds volledig verdwenen

Patients will be asked to score their recurrence of symptoms at week 26.

References

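### VAS and RQLQ are measured twice before treatment, but the model names one undefined baseline value; entering both readings as separate covariates would be a cheap, modest gain in precision

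*Combined protocol and SAP*

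**What the plan says.** Methodology, section D (Statistics), specifies a longitudinal linear model with an unstructured covariance matrix. It "will be used to compare the evolution of VAS, RQLQ and drop in PNIF between the four groups", "with the baseline value as a covariate". The section does not define that value further.

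Section H (Time schedule and visit table) has two visits before the treatment visit, "Screening visit (week -3" and "Baseline visit (week -1" in its notation. Each lists "Symptom evaluation using VAS scores for individual and total nasal symptoms" and also the RQLQ, and Table 3 marks both columns for both instruments. PNIF and the cold dry air challenge are done before treatment at week -1 only.

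Section I (Variables) does not settle which reading is meant. It asks for "total nasal symptoms (TNS) before treatment and at week 4, 12 and 26" on the VAS, and for the RQLQ says: "Patients will be asked to score RQLQ before treatment and at week 4, 12 and 26". The only stated use of a pre-treatment score outside the model is the inclusion criterion of 5 or more for total nasal symptoms (TNS) on the VAS.

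**The concern.** A single VAS or RQLQ reading is noisy. Two readings taken before randomisation usually predict the follow-up value better than one, and adjusting for both leaves the randomised comparison unbiased. If the covariate is the week -1 value alone, the week -3 scores are collected from every patient and then not used in the analysis. If it is left undefined, two analysts could fit different models.

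What is at stake is the width of the intervals. The sample size comes from expected recruitment. The trial's product is a set of 95% confidence intervals, set against a 1-point region for VAS and intended to inform a larger trial. Any narrowing that needs no extra patient or visit is useful.

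**Working it through.** **Plan's own figure.** Only 4 × 30 = 120 can be checked, and it agrees. The documents give no SD, correlation, alpha or power, so there is no power calculation to reproduce.

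**Inputs.** From the documents: 120 patients and a possible 10% dropout, hence 120 × 0.9 = 108 completers, or 27 per arm. Assumed: r, the correlation of a pre-treatment reading with the follow-up value, and rb, the correlation between the two pre-treatment readings.

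**Formulas** (residual variance as a fraction of outcome variance):
- one baseline: 1 − r²
- two separate baselines: 1 − (r1² + r2² − 2·r1·r2·rb)/(1 − rb²), which becomes 1 − 2r²/(1 + rb) when r1 = r2 = r
- mean of the two: 1 − (r1 + r2)²/(2(1 + rb))

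**Cost of the extra covariate.** Four groups and one covariate leave 108 − 5 = 103 residual degrees of freedom; a second covariate leaves 102. As an approximation, estimating it costs 1/102, or about 1% in variance.

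**Equal predictors.** Net ratio = gross ratio × (1 + 1/102).

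| r | rb | one | two | gross fall | net fall |
|---|---|---|---|---|---|
| 0.5 | 0.6 | 0.7500 | 0.6875 | 8.3% | 7.4% |
| 0.5 | 0.7 | 0.7500 | 0.7059 | 5.9% | 5.0% |
| 0.4 | 0.6 | 0.8400 | 0.8000 | 4.8% | 3.8% |
| 0.4 | 0.7 | 0.8400 | 0.8118 | 3.4% | 2.4% |

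A net fall of 2% to 7% corresponds to 120/0.98 − 120 = 2.4 up to 120/0.93 − 120 = 9.0 patients. The standard error falls by 1 − √0.98 = 1.0% up to 1 − √0.93 = 3.6%.

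**Week -3 the weaker predictor** (0.5 at week -1, 0.4 at week -3, rb 0.7):
- two separate covariates: 1 − (0.25 + 0.16 − 0.28)/0.51 = 0.7451 against 0.7500. That is 0.7% lower gross and nil after the 1% cost.
- mean: 1 − 0.81/3.4 = 0.7618, which is 1.6% higher than week -1 alone.

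**Entry threshold.** A simulation kept only patients with screening TNS of 5 or more (assumed SD 2, population mean 5 to 7). At r 0.5 and rb 0.7 the gross gain for TNS falls from 5.9% to about 3% to 4.5%. At r 0.5 and rb 0.6 it falls from 8.3% to about 4% to 6%. The 1% cost comes off these as well. The criterion sets no direct cut-off on RQLQ or on the individual-symptom scores.

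**Interval width.** With an assumed SD of 2.5, 27 per arm, r 0.5 and rb 0.7, the 95% half-width for a difference goes from 1.17 to 1.13, before the 1% cost and before any loss from the threshold.

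**The case against.** Adjusting for one pre-treatment value is conventional and valid. It introduces no bias and contradicts nothing, and the plan says that its intervals describe the differences and are not meant to establish non-inferiority. The size of any gain rests wholly on assumed correlations. Week -3 is further from every outcome visit and may predict less well, and total nasal symptoms at screening are selected by the entry rule. In the example the half-width stays above the 1-point region with either model, so no conclusion would turn on the change.

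The documents also leave open how the first-listed outcome, VAS for the major symptom, is obtained at each visit. The visits list individual and total symptoms only, and nothing says when the major symptom is chosen or whether it stays fixed.

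All of this stands as a limit on the size of the gain, but it does not remove the point. A descriptive pilot is only as informative as its intervals are narrow, the second reading is already scheduled, and the covariate needs defining in any case.

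**Conclusion.** The point holds as an efficiency suggestion joined to a missing definition. Under the assumed correlations (0.4 to 0.5 with the outcome, 0.6 to 0.7 between readings) the net reduction in residual variance is roughly 2% to 7%. It is less for total nasal symptoms and about nil if week -3 is clearly the weaker predictor. No stated figure changes, and the PNIF drop is unaffected because it has one pre-treatment measurement.

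Three stronger readings are tempting, and the documents do not support them:
- **That the plan discards the week -3 scores.** The baseline value is undefined. Week -1 is the natural reading, but a mean of the two is not excluded.
- **That the gain is large.** With r = rb = 0.7 the formula gives 0.4235 against 0.5100, a 17.0% fall, worth 120 × 0.5100/0.4235 − 120, or about 25 patients. That needs two untreated readings two weeks apart to correlate no better than a week -1 reading does with one taken 5 to 27 weeks later, after treatment. It also ignores the entry threshold.
- **That the gain is free.** The extra covariate costs about 1% in variance, and averaging the two readings can lose precision.

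**What to change.** Before unblinding, add a sentence to Methodology, section D, that defines the baseline covariates:
- For each VAS and RQLQ outcome, enter the week -3 and week -1 values of that same outcome as two separate covariates. Do not use their mean.
- For the major-symptom VAS, state how the symptom is designated, and take the same symptom at both visits.
- For the PNIF drop, keep the week -1 value alone.
- State whether baseline effects are common to all follow-up visits or vary by visit.

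This is a cheap improvement that adds no visit, procedure or patient. The cost is one extra covariate per model, about 1% in variance at about 108 completers, and more if covariate-by-visit terms are used (three parameters with three follow-up visits).

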- To evaluate if two novel treatment modalities (explained more briefly on page 9 in paragraph 'Study Onset' of chapter 'Methodology') show non-inferiority on subjective evaluations (symptom score on a Visual Analogue Scale (VAS), Therapeutic Response Evaluation (TRE) and Rhinitis Quality of Life Questionnaire (RQLQ)) compared to the current treatment modality of capsaicin nasal treatment in patients with IR. The gathered data of this single center trial can be used to guide the decision on the set-up and the design of a larger multi-center trial being powered to prove non-inferiority.

Our secondary aims are:

- To evaluate if the two novel treatment modalities show non-inferiority compared to the current treatment modality of capsaicin nasal treatment in patients with IR on objective evaluations (Peak Nasal Inspiratory Flow (PNIF) measurements before and after CDA challenge).
- To evaluate the occurrence of adverse events at week 4, week 12 and week 26 and recurrence of symptoms and NHR at week 26 in the different treatment groups.

B. Hypothesis

Non-inferiority in efficacy of the two novel treatment regimes i.e. capsaicin nasal spray 0,01mM (2puffs/nostril/day) during 4 weeks and capsaicin nasal spray 0,001mM (2puffs/nostril/day) during 4 weeks compared to the current treatment of capsaicin nasal spray 0,1mM (5/day administered on a single day) with regard to the scores on week 4 (taking into account the baseline level).

C. Outcome

- VAS for major nasal symptom at week 4, week 12 and week 26. The region of equivalence is defined as a difference in VAS of less than 1.
- VAS for total and individual nasal symptoms at week 4, week 12 and week 26. The region of equivalence is defined as a difference in VAS of less than 1.
- TRE (based on a scale from 1 to 5) at week 4, week 12 and week 26. The region of equivalence is defined as a difference in percentage for patients of less than 10% in all different TRE scoring groups.

- NHR (objectively measured by PNIF before and after CDA challenge) in all treatment modalities at week 4, week 12 and week 26. The region of equivalence is defined as a drop in PNIF of less than 10%.
- Appearance of adverse events at week 4, week 12 and week 26.
- Recurrence of symptoms (based on a scale of 1 to 5) at week 26.

Study design

A. Type of study

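### TRE is analysed by a logistic GEE with no stated missing-data handling or working correlation, so its week-12 and week-26 comparisons may be biased if dropout depends on earlier response and differs between arms

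*Combined protocol and SAP*

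**What the plan says.** Methodology, D. Statistics, uses two methods. For the continuous outcomes, a linear longitudinal model "will be used to compare the evolution of VAS, RQLQ and drop in PNIF between the four groups, with the baseline value as a covariate", and "a direct likelihood approach is adopted using an unstructured covariance matrix"; a textbook on missing data is cited for this. For TRE, a "logistic regression model using generalized estimating equations (GEE") "will be used to compare the evolution in proportion patients free of complaints (TRE score 5), with the baseline TRE score as covariate". Nothing is said about weights, imputation, the working correlation or a missing-data sensitivity analysis for TRE.

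Methodology, C. Sample size and setting, notes: "A drop out rate of 10% due to concomitant infection, loss of follow-up or non-related adverse events is possible during the setting". The figure is not split by arm or by response.

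Under I. Variables, the TRE entry says: "Patients will be asked to score their symptom relief on week 4, week 12 and week 26". The visit overview (Table 3) agrees: TRE is marked at the three follow-up visits only. The lowest TRE category is defined relative to the state before treatment, so the scale has no meaning at baseline.

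In Objectives, TRE is one of the three subjective evaluations in the primary aim. The hypothesis is framed "with regard to the scores on week 4 (taking into account the baseline level"), while section C. Outcome lists TRE at weeks 4, 12 and 26 with a region of equivalence of 10 percentage points.

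**The concern.** Direct likelihood uses each patient's earlier observed values, so it tolerates dropout that depends on them. Ordinary GEE does not in general. It needs dropout to be completely random or explained by covariates in the model. The one patient-level covariate named for TRE is a baseline TRE score, which is never measured and so can explain nothing. Dropout after week 4 that follows week-4 response would be left uncorrected, except for whatever the unstated working correlation happens to recover.

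Two things are at stake. First, VAS, RQLQ and TRE from the same patients would rest on different missing-data assumptions, with the stronger one applied to TRE. Second, if patients without relief leave more often in one arm than another, the later proportions free of complaints rise more in that arm. The shift goes into the novel-versus-current difference that is to be set against the 10-point region and used in planning a larger trial.

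**Working it through.** The plan gives no TRE response rate, no dropout by arm and no bias figure, so there is no number to reproduce. The size below rests on assumptions.

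**Inputs from the plan.** 30 patients per arm; about 10% dropout, so 30 × 0.10 = 3 lost and 27 completers per arm; a region of 10 points; 95% confidence intervals.

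**Assumed.** True TRE = 5 rate p of 20–40%, equal in the two arms compared; within-patient correlation of the underlying response 0.5–0.9; dropout after week 4 confined to the lowest 40% of week-4 scores.

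**Independence working correlation.** With a separate mean for each arm and visit, the GEE estimate is the available-case proportion. Let d be the dropout fraction and q the later TRE = 5 rate in the group that dropouts come from. The observed proportion is (p − dq)/(1 − d), so each arm is inflated by (p − q) × d/(1 − d). With equal p and q in both arms:

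bias in the difference = (p − q) × [d_new/(1 − d_new) − d_ref/(1 − d_ref)]

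- 5% vs 15%: 0.15/0.85 − 0.05/0.95 = 0.124.
- 0% vs 20%: 0.20/0.80 − 0 = 0.25.
- 10% vs 10%: 0.

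The upper bound is q = 0 (no dropout would have become free of complaints). At p = 30% it is 0.30 × 0.124 = 3.7 points and 0.30 × 0.25 = 7.5 points. Under the assumed correlations, simulation puts p − q at about 0.13 to 0.37.

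**Exchangeable working correlation.** There is no simple formula. The figures come from large simulated samples on the same type of scenario and carry a few tenths of a point of simulation error.

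Bias in the week-26 difference, in percentage points (positive favours the novel arm; the sign reverses if dropout is higher in the reference arm):

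| Dropout, reference vs novel | Bound, q = 0 | Independence GEE | Exchangeable GEE |
|---|---|---|---|
| 10% vs 10% | 0 | 0 | about 0 |
| 5% vs 15% | 2.5–5.0 | 1.6–4.6 | about 0.5–1.2 |
| 0% vs 20% | 5.0–10.0 | about 3–9 | about 1.5–2.5 |

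**Unequal true rates.** With 10% dropout in both arms and true rates of 30% and 20%, the bound is (0.20 − 0.30)/0.9 = −11.1 points against a true −10, a bias of −1.1.

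**Dropout that depends on the recorded TRE = 5 status itself.** At 30% in both arms and 0% vs 20% dropout, a second simulation gave +3.6 points with independence GEE, +0.1 with exchangeable GEE and +0.2 with a MAR-valid estimator. An exchangeable structure thus removes nearly all the bias when dropout follows the modelled indicator. It removes less when dropout follows the underlying severity, which that indicator summarises coarsely.

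**Week 4.** All methods gave the same week-4 estimate. It is the first visit with a TRE score, so a likelihood model for TRE alone would have no earlier TRE to use either.

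**Sampling error for scale.** With 27 completers per arm the half-width is 1.96 × √(2p(1 − p)/27): 16 points at p = 10%, 24 at 30%, 27 at 50%.

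**The case against.** The case for leaving the plan alone has real force.

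- A reader might infer that the TRE comparison is biased. The documents do not show that. The listed reasons for dropout are infection, loss to follow-up and unrelated adverse events. Lack of effect is not among them, and only loss to follow-up could plausibly carry it. The bias needs response-related dropout that also differs by arm.
- A reader might expect unequal dropout because some arms spray daily and one is treated on a single day. The double-dummy design rules that out as a reason: every arm receives five blinded applications and then a blinded daily spray for four weeks. Differences in efficacy or irritation could still produce it.
- A reader might conclude that the hypothesis is compromised. It concerns week 4, which is essentially unaffected.
- A reader might take direct likelihood as protection against any loss of non-responders. If patients leave because of a response that was never recorded, the data are missing not at random and direct likelihood is not protected either.
- That the GEE is unweighted is inferred from silence, though it is the ordinary reading of the sentence. The larger bias figures also presume an independence structure that the plan does not state.
- The study is a descriptive pilot, and its confidence intervals are far wider than the likely bias.

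These points limit the size and certainty of the problem. What stands is that the TRE sentence leaves the missing-data assumption and working correlation open, names a covariate that will not exist, and does not match the care taken for the other outcomes. A wide interval does not justify an avoidable shift in a point estimate meant to inform a later trial.

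**Conclusion.** The point holds as a specification gap with a conditional consequence. As written, the TRE analysis is not generally valid under the MAR assumption that suffices for VAS, RQLQ and PNIF, and this matters for weeks 12 and 26 only. With dropout split 5% vs 15%, the TRE difference may shift by about 1.6–4.6 points under independence GEE or 0.5–1.2 under exchangeable GEE. An extreme 0% vs 20% split gives about 3–9 or 1.5–2.5 points. With equal dropout and equal true rates it is about zero. All of these rest on assumed response rates of 20–40% and on dropout confined to poor week-4 responders; none comes from the documents. Only strongly unequal dropout would use up much of the 10-point region, and sampling error is larger in every case considered. Severity is low; this is a cheap improvement.

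**What to change.** Rewrite the TRE sentence in D. Statistics to state:

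- **Assumption.** TRE missing at weeks 12 and 26 is treated as MAR given arm and earlier observed outcomes, in line with the other outcomes.
- **Method.** Multiply impute missing week-12 and week-26 TRE from arm, earlier TRE on its five-point scale, VAS and RQLQ. Then derive TRE = 5, fit the planned logistic GEE and pool the results.
- **Working correlation.** Name it.
- **Covariate.** Remove baseline TRE. If baseline adjustment is wanted, use a value that is collected, such as baseline VAS.
- **Sensitivity.** Keep the unweighted GEE on observed data. Counting dropouts as not free of complaints would be a simple further check on departures from MAR.

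Report dropout by arm and by week-4 TRE, so that readers can see whether the conditions for bias arose.

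Multiple imputation is preferable to inverse-probability weighting here, because about three dropouts per arm cannot support a model for the probability of dropout. The cost is a few lines of text and some programming, with no new data. The drawback is reliance on an imputation model fitted to few patients, so it should be kept small.

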- Systemic steroid treatment less than 4 weeks before the inclusion in the study, nasal steroid spray less than 4 weeks before the inclusion, oral leukotriene antagonists or long-acting antihistamines less than 2 weeks before the inclusion.
- Inability of the patient to stop taking medication affecting nasal function like β -blockers.
- History of prolonged use or abuse of decongestant nasal spray like xylometazoline spray and/or use or abuse of decongestive oral medication.
- Evidence of infectious rhinitis/rhinosinusitis or common cold within 4 weeks prior to inclusion.

- Pregnancy or lactation. **
- Any disorder of which might compromise the ability of a patient to give truly informed consent for participation in this study.
- Enrollment in other investigational drug trial(s) or receiving other investigational agent(s) for any other medical condition.
- Contra-indications for the use of local anesthesia (cocaine 5%).
- Smoking or occupational exposure to irritants (like hypochlorite, persulfates, isocyanates).
- Nasal malignancies or severe comorbidity like granulomatosis or vasculitis.

*Note *:*

Patients with underlying allergic disease are defined by positive skin prick test for the 18 most prevalent inhalant allergens (house dust mite, timothy grass, smooth meadow grass, orchard grass, nettle, plantago, oxeye daisy, mugwort, alder, birch, hazel, horse, cat, dog, rabbit, Alternaria, Aspergillus and Cladosporium - HAL Allergy, Leiden, The Netherlands) and/or positive IgE analysis in the blood.

*Note **:*

Female patients with childbearing potential will be offered a pregnancy test at the screening.

D. Possible hurdles

Based on the former studies in which the therapeutic effect of capsaicin is proven (9) (10) (11) (12) (13) (18) and given the fact that capsaicin is well tolerated and side effects are minimal, it is very unlikely to be subject of foreseen or unforeseen obstacles in the elaboration of this study protocol. Beside minor inconveniences such as rhinorrhea, sneezing and watery eyes, there are no other known side effects.

With regard to the safety of all individuals, the study will immediately be abrogated and the treatment protocol we will un-blinded at once, in case of any allergic reaction or any other adverse event.

Methodology

A. Study onset

This study will include 4 parallel arms of equal sample size.

120 IR patients will be included in this four-arm study (n=30 patients per treatment arm).

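### The only planned model for TRE is score 5 versus the rest, so four of the five category margins have no matching model, and information and estimability depend on a score-5 rate the plan does not give

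*Combined protocol and SAP*

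**What the plan says.** Objectives, A. Aims lists TRE with VAS and RQLQ among the subjective evaluations of the primary aim. Methodology, I. Variables states that "TRE will be measured on a 1 to 5 scale". The top level is "5 klachten zijn volledig verdwenen" (complaints completely gone), level 4 means almost completely gone, and level 1 means unchanged. TRE is scored at weeks 4, 12 and 26.

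Objectives, C. Outcome sets the TRE region of equivalence as a between-group difference of less than 10% of patients, and applies it to all of the TRE scoring groups. Methodology, D. Statistics says that group differences will be compared with these regions. For TRE it names one model, a logistic GEE that "will be used to compare the evolution in proportion patients free of complaints (TRE score 5". It names no ordinal model, expected score-5 rate, or method for sparse cells.

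On size, Methodology, A. Study onset says "120 IR patients will be included in this four-arm study (n=30 patients per treatment arm". Methodology, C. Sample size and setting adds "A drop out rate of 10% due to concomitant infection, loss of follow-up or non-related adverse events is possible during the setting".

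**The concern.** The model and the criterion do not match. The criterion concerns the percentage of patients in each of five categories, while the model estimates one of them. A patient at level 4 is treated the same as a patient at level 1. This mismatch is in the text and depends on no assumed event rate.

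Two further consequences depend on how many patients reach score 5. If few do, a top-category cut uses little of the information in the five-level score. In small arms, some arm-by-visit cells may also contain no event, and the corresponding odds ratio then has no finite estimate. Because the pilot is meant to guide the design of a larger non-inferiority trial, the TRE pattern it reports should use the data collected.

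**Working it through.** **Inputs from the plan.** There are four equal arms: "This study will include 4 parallel arms of equal sample size". 4 × 30 = 120 agrees with the stated total. The possible 10% drop-out gives 30 × 0.90 = 27 evaluable per arm. The 120 cannot be re-derived by formula, because it is a recruitment forecast: "Based on previous experience in the center, the expected total number of IR patients equals 120 taking into account a recruitment period of three years".

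**Assumed.** The TRE distributions, since the documents give none. Both arms are given the same distribution, at one visit.

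**Precision.** With n = 27 per arm and p the score-5 rate, the variance of the log odds ratio for score 5 versus the rest is 2 / [n p(1−p)]. For the proportional-odds model on all five levels (Whitehead) it is 12 / [N(1 − Σp_i³)] with N = 54. The share of information the cut keeps is the ratio of the second variance to the first, 3p(1−p) / (1 − Σp_i³).

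| Assumed % at levels 1/2/3/4/5 | Σp_i³ | SE, score 5 only | SE, five levels | Share kept |
|---|---|---|---|---|
| 35/25/20/15/5 | 0.0700 | √(2/1.2825) = 1.25 | √(12/50.22) = 0.49 | 15% |
| 10/20/35/25/10 | 0.0685 | √(2/2.43) = 0.91 | √(12/50.30) = 0.49 | 29% |
| 10/10/20/30/30 | 0.0640 | √(2/5.67) = 0.59 | √(12/50.54) = 0.49 | 67% |

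In the 10% row, matching the five-level precision from score 5 alone would take about 27 / 0.29 = 93 per arm.

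The half-way point: with 20% at every level, 3 × 0.2 × 0.8 / (1 − 5 × 0.008) = 0.48 / 0.96 = 50%. If the other scores cluster heavily on one level, the share is already about 49% at a 15% rate. So more than half is lost below about 15% to 20%, depending on the spread of levels 1 to 4.

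**Empty cells.** The chance of no score-5 patient in one arm at one visit is (1−p)^27. The chance that at least one of four arms is empty at that visit, if all share the rate, is 1 − [1 − (1−p)^27]^4.

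| True score-5 rate | One given arm | Any of four arms |
|---|---|---|
| 2% | 58% | 97% |
| 5% | 25% | 68% |
| 10% | 5.8% | 21% |
| 20% | 0.2% | 1% |

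Which figure matters depends on the model. Comparing an evolution and reporting differences at specific time points suggests arm-by-visit terms, where one empty visit is enough. A single pooled arm effect fails only if the arm is empty at all three visits. In a simulation with three correlated visits (assumed latent correlation 0.6), a given arm was empty at one or more visits in 52% of runs at a 5% rate and 15% at a 10% rate. It was empty at all three in 4% and 0.2%.

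**What software does.** In one simulated data set with an arm that had no events, a main-effects logistic GEE gave a log odds ratio of about −25 to −28 for that arm with a standard error of about 0.46, and reported convergence. The failure is therefore not always flagged.

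**The case against.** Being free of complaints is a pre-specified, labelled and clinically readable category, and the plan says that "The current study is not designed to prove non-inferiority, but serves as a pilot study". A common odds ratio has no margin in the documents, and its gain in precision assumes proportional odds. These points stand. They are reasons to keep score 5 as a reported result and to rest the margin comparison on percentages. They do not supply a model for the other four categories.

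Three stronger readings are tempting, and the documents do not support them.

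- A reader might infer that the cut discards most of the TRE information. That holds only at low score-5 rates. At 30% about two-thirds is kept and the standard error is 0.59 against 0.49. The documents give no rate. The background describes the earlier 14-patient study as showing a strong effect but gives no proportion.
- A reader might infer that a shift from level 4 to level 2 would go unseen. VAS and RQLQ are modelled longitudinally beside TRE, and the Outcome section calls for percentages in every category, where such a shift would show. What is missing is a named model for those percentages.
- A reader might infer that an empty arm defeats the TRE comparison. One empty arm gives quasi-complete separation of that arm's coefficient. If placebo is empty, the hypothesised comparisons of Groups II and III with Group I remain estimable. The margin is on the percentage scale, and a difference in proportions can still be reported.

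**Conclusion.** The point holds in this form. The planned TRE model covers one of the five categories to which the plan's own margin applies. That part needs no assumption.

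The size of the other two effects is conditional. The cut loses more than half of the proportional-odds information only if fewer than about 20% reach score 5. Empty cells deserve a stated fallback at rates of about 10% or lower and are negligible at 20% or more. These figures rest on 27 evaluable patients per arm, one visit, assumed score distributions and proportional odds. The multi-visit figures also rest on the assumed correlation. The consequence is limited to the TRE analysis of a descriptive pilot, but it is worth correcting because the data are already collected.

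**What to change.** In Methodology, D. Statistics, make the main TRE analysis a repeated-measures cumulative-logit (proportional-odds) model on all five levels, with group, visit and group-by-visit. Report the common odds ratio. For each visit, also report observed and model-based percentages per category, with between-group differences and 95% confidence intervals, set against the margin in Objectives, C. Outcome. Keep the score-5 proportion as a supportive result, and name a penalised or exact method for use if a cell is empty.

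The cost is SAP wording and standard software, with no new data or visits. There are two downsides. The proportional-odds assumption must be checked. The common odds ratio has no margin of its own, so the comparison with the margin rests on the category percentages. Those will be imprecise: with 27 per arm and a 10% observed rate in both arms, the 95% half-width for a simple difference is 1.96 × √(2 × 0.10 × 0.90 / 27) = 0.16, or 16 percentage points, which exceeds the 10% margin. That comparison should therefore be presented as descriptive, as the plan already intends.
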